## **PROTOCOL AMENDMENT, VERSION 8: RATIONALE**

Protocol GX28228, Version 8 has been amended primarily to reflect the extension of study duration for patients in the intravitreal ranibizumab control arm. Changes to the protocol, along with a rationale for each change, are summarized below.

- Study duration for patients in the intravitreal ranibizumab control arm has been extended by approximately 4 months to align with the other treatment arms and to allow for continued monthly evaluation and study treatment until the Sponsor decides, based on the primary analysis results, to either terminate the study and discontinue study treatment, or offer patients entry into the Ranibizumab Port Delivery System (RPDS) Extension Study. Primary analysis data is expected to be available approximately 4 months after the Month 9 visit of the last patient randomly assigned in the study. The study duration extension for this control arm aligns the duration of patient participation for all study treatment arms at approximately 13–38 months, dependent on the date of the patient's randomization to the study (Sections 3.1 and 4.6.10.5, Figure 2, and Table 3).
- "RPDS Extended Use Life Study" has been replaced with "RPDS Extension Study" (Sections 3.1, 3.2, 4.4.2, and 4.6.10.5, and Appendix 1).
- The Secondary Medical Monitor information has been updated (Section 5.4.1).

Additional minor changes have been made to improve clarity and consistency. Substantive new information appears in italics. This amendment represents cumulative changes to the original protocol.

## PROTOCOL SYNOPSIS

**TITLE:** A PHASE II, MULTICENTER, RANDOMIZED, ACTIVE TREATMENT–CONTROLLED STUDY OF THE EFFICACY AND SAFETY OF THE RANIBIZUMAB PORT DELIVERY SYSTEM FOR SUSTAINED DELIVERY OF RANIBIZUMAB IN PATIENTS WITH SUBFOVEAL NEOVASCULAR AGE-RELATED MACULAR DEGENERATION

**PROTOCOL NUMBER:** GX28228

**VERSION NUMBER:** 8

**EUDRACT NUMBER:** Not applicable

**IND NUMBER:** 113,552

**TEST PRODUCT:** Ranibizumab Port Delivery System for Sustained Delivery of Ranibizumab (RO4893594)

**PHASE:** II

**INDICATION:** Subfoveal neovascular age-related macular degeneration

**SPONSOR:** Genentech, Inc.

### Objectives

#### **Efficacy Objectives**

The primary efficacy objective for this study is as follows:

- To evaluate the relative efficacy of 10-mg/mL, 40-mg/mL, and 100-mg/mL formulations of ranibizumab, delivered via the Implant, as measured by the time a patient first requires Implant refill according to protocol-defined refill criteria

The secondary efficacy objectives for this study are as follows:

- To evaluate and compare the relative efficacy of 10-mg/mL, 40-mg/mL, and 100-mg/mL formulations of ranibizumab, delivered via the Implant, to that of 10-mg/mL (0.5-mg dose) monthly ITV ranibizumab injections, as measured by the change in BCVA from baseline at Month 9
- To evaluate the efficacy of 10-mg/mL, 40-mg/mL, and 100-mg/mL formulations of ranibizumab, delivered via the Implant, with that of 10-mg/mL (0.5-mg dose) monthly ITV ranibizumab injections over time, as measured by the change in BCVA from baseline over time
- To evaluate the efficacy of 10-mg/mL, 40-mg/mL, and 100-mg/mL formulations of ranibizumab, delivered via the Implant, with that of 10-mg/mL (0.5-mg dose) monthly ITV ranibizumab injections over time, as measured by the change in central foveal thickness (CFT, defined as the retinal thickness in the center of the fovea) from baseline over time
- To evaluate the functionality of the Implant by assessing that there is no evidence of Implant clogging in more than 10% of patients in the Implant arms at Month 9

### **Safety Objectives**

The safety objectives for this study are as follows:

- To evaluate the safety of ranibizumab delivered via the Implant, compared with that of monthly ITV injection, as measured by ocular and non-ocular adverse events and serious adverse events
- To evaluate the safety of the Ranibizumab Port Delivery System (RPDS), as measured by “Prespecified RPDS-associated adverse events”
- To evaluate the proportion of patients with positive serum antibodies to ranibizumab

### **Pharmacokinetic Objectives**

The pharmacokinetic (PK) objectives for this study are as follows:

- To characterize the serum pharmacokinetics of ranibizumab in patients after the initial fill and subsequent refills in the Implant treatment arms

### **Exploratory Objectives**

The exploratory objectives for this study are as follows:

- To evaluate the development of macular atrophy in all three Implant treatment arms relative to one another and to the monthly ITV arm
- To examine the impact of ranibizumab treatment on patient-reported treatment satisfaction as assessed by the Macular Degeneration Treatment Satisfaction Questionnaire (MacTSQ) at Months 1, 6, 9, and the final or early termination visit for patients who speak English or Spanish
- To explore time to subsequent Implant refills according to protocol-defined refill criteria
- To describe the number of times patients meet protocol-specified refill criteria
- To evaluate the proportion of patients in each Implant arm who first meet the protocol-defined refill criteria prior to and at Months 4, 5, and 6
- To evaluate the proportion of patients with an improvement of  $\geq 15$  letters in BCVA from baseline
- To evaluate the proportion of patients with a loss of  $\geq 15$  letters in BCVA from baseline over time
- To explore the utility of BCVA measured under low luminance as a predictor of treatment benefit over time
- To evaluate the changes in total lesion area, area of CNV lesion, and CNV leakage over time, as assessed by fluorescein angiography
- To explore the serum ranibizumab concentration data with a PK model in an attempt to infer the concentration–time pattern in the vitreous or aqueous humor and, if possible, derive information on the rate of ranibizumab release from the Implant
- To characterize ranibizumab aqueous humor concentration over time (optional)
- To characterize ranibizumab vitreous or aqueous humor concentration after Implant explantation (if applicable)
- To evaluate the potential association of circulating biomarkers with disease characteristics and response to ranibizumab (optional)
- To evaluate the relationship of genetic variants (such as AMD risk alleles; polymorphisms within the complement pathway; and polymorphisms within the VEGF-A genetic locus) with the disease characteristics and/or response to treatment with ranibizumab (optional)
- To evaluate the potential association of vitreous or aqueous humor biomarkers with disease characteristics and/or response to ranibizumab
- To evaluate the proportion of patients meeting lack of clinical efficacy criteria
- To evaluate the proportion of patients requiring explantation
- To evaluate the changes in CNV perfusion over time as assessed by OCT Angiography (at selected sites that have OCT angiography equipment)

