### **Exploratory Outcome Measures**

The exploratory outcome measures for this study are as follows:

- Treatment emergent macular atrophy in all treatment arms
- The MacTSQ score at randomization and at Months 1, 6, 9, and the final or early termination visit for patients who speak English or Spanish
- Time to subsequent Implant refills according to protocol-defined refill criteria
- Number of times a patient meets protocol-specified refill criteria
- Proportion of patients in each Implant arm who first meet the protocol-defined refill criteria prior to and at Months 4, 5, and 6
- Proportion of patients with an improvement of BCVA from baseline of  $\geq 15$  letters over time
- Proportion of patients losing  $\geq 15$  letters in BCVA from baseline over time
- Change in BCVA from baseline over time measured under low luminance conditions

- Changes from screening in total lesion area, area of CNV lesion, and CNV leakage over time, as assessed by fluorescein angiography
- Proportion of patients meeting lack of clinical efficacy criteria
- Proportion of patients requiring explantation
- Changes in CNV perfusion over time, as assessed by OCT Angiography

In addition, vitreous samples from the Refill Needle (if applicable), optional aqueous humor samples, and optional serum and plasma samples may be collected to assess the relationship between biomarkers and the disease characteristics and/or response to treatment with ranibizumab. Optional whole blood samples will be collected for DNA extraction (genetic analysis) to assess the relationship between genetic variants and the disease characteristics and/or response to treatment with ranibizumab.

In addition, vitreous or aqueous humor samples before Implant explantation, and optional aqueous humor samples prior to or immediately following one or more refills and at the Day 7 safety visit post refill will be collected to characterize ranibizumab vitreous and aqueous humor concentration.

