## **6.8 EXPLORATORY ANALYSES**

Detailed specifications of the statistical methods for the exploratory analyses will be described in the SAP.

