### **2.2.5 Exploratory Efficacy Outcome Measures**

The exploratory outcome measures are as follows:

- Treatment emergent macular atrophy in all treatment arms
- The Macular Degeneration Treatment Satisfaction Questionnaire (MacTSQ) score at randomization and at Months 1, 6, 9, and the final or early termination visit for patients who speak English or Spanish
- Time to subsequent Implant refills according to protocol-defined refill criteria
- Number of times a patient meets protocol-specified refill criteria
- Proportion of patients in each Implant arm who first meet the protocol-defined refill criteria prior to and at Months 4, 5, and 6
- Proportion of patients with an improvement of BCVA from baseline of  $\geq 15$  letters over time

- Proportion of patients losing  $\geq 15$  letters in BCVA from baseline over time
- Change from baseline in BCVA over time measured under low luminance conditions
- Changes from screening in total lesion area, area of choroidal neovascularization (CNV) lesion, and CNV leakage over time, as assessed by fluorescein angiography
- Proportion of patients meeting LCE criteria
- Proportion of patients requiring explantation
- Changes in CNV perfusion over time, as assessed by optical coherence tomography (OCT) angiography

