### **4.4 EFFICACY ANALYSIS**

Efficacy analyses will be done using the modified ITT population. Although this study is powered based on the log-rank test at a one-sided significance level of 15% for the primary outcome measure, there is no prespecified alpha level for other outcome

measures. 95% CIs will be reported for estimation purposes and for treatment arm differences unless stated otherwise. No adjustments will be made for multiplicity. Except for the primary endpoint, no statistical tests will be conducted. All analyses will be based on observed results unless imputation of missing data is specified. For the analysis purpose, the stratification factors as recorded in IxRS will be used if there is a discrepancy between the CRF and the IxRS data.

Unless otherwise specified, continuous variables will be summarized using descriptive statistics including mean, standard deviation, median, and range. Categorical variables will be summarized using counts and percentages.

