#### **Additional Efficacy Analyses Focused on BCVA Parameters**

- The mean average change from baseline through Month 9 (AUC-like endpoint) in BCVA and 95% CIs will be generated for each treatment arm.
- Summary statistics and figures by treatment arm showing the proportion of patients losing <15 letters, <10 letters, <5 letters, and <0 letters over time through Month 10 will be provided.
- Change from baseline in BCVA over time through Month 10 measured under low luminance conditions will be summarized by treatment arm using descriptive statistics.

Data for patients who receive rescue treatment or undergo explantation prior to Month 9 will be censored. Missing data will not be imputed.

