#### **4.4.2.4 Other Exploratory Efficacy Endpoints**

Other exploratory efficacy endpoints listed in Section 2.2.5 will be summarized using descriptive statistics. Observed data will be used.

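### Low-luminance BCVA is to be explored as a predictor of treatment benefit, but the outcome measure and the only planned analysis treat it as a response

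*Protocol*

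**What the plan says.** The objective appears in the protocol synopsis, in Protocol 2.4 and in the synopsis reprinted as SAP Appendix 1: "To explore the utility of BCVA measured under low luminance as a predictor of treatment benefit over time".

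The matching outcome measure in Protocol 3.5.5 and the synopsis is "Change in BCVA from baseline over time measured under low luminance conditions". SAP 2.2.5 carries it over as "Change from baseline in BCVA over time measured under low luminance conditions".

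For methods, Protocol 6.8 defers: "Detailed specifications of the statistical methods for the exploratory analyses will be described in the SAP". SAP sections 1 and 2.1 state that the SAP's analyses replace those in the protocol. The SAP's one rule for this variable is in 4.4.2.1, among the additional BCVA analyses: "Change from baseline in BCVA over time through Month 10 measured under low luminance conditions will be summarized by treatment arm using descriptive statistics". Patients rescued or explanted before Month 9 are censored, and missing values are not imputed. The content of such a summary is set in SAP 4.4, where "continuous variables will be summarized using descriptive statistics including mean, standard deviation, median, and range". The same section adds "Except for the primary endpoint, no statistical tests will be conducted". The catch-all for the remaining exploratory endpoints in SAP 4.4.2.4 is also descriptive: "Other exploratory efficacy endpoints listed in Section 2.2.5 will be summarized using descriptive statistics".

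Protocol Appendices 1 and 2 schedule low-luminance testing at screening, randomization and every monthly visit in all arms, and also at the safety visits in the Implant arms.

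**The concern.** A predictor and a response are different roles. To explore prediction, a patient's low-luminance BCVA must be linked to that patient's later result on a stated measure of benefit. The outcome measure and the SAP summary instead ask how low-luminance BCVA itself changes in each arm. That is a legitimate question, but not the one in the objective. The objective also leaves benefit undefined, and the SAP does not supply a definition.

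If nothing changes, the study report will have a stated objective and no result to set against it. Any analysis added later would choose its predictor and its benefit measure after efficacy data had been seen. Two interim efficacy analyses have already been done (SAP 4.8).

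**Working it through.** The plan gives no figure for this objective, so there is none to reproduce. The check has three parts.

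**1. Is the link made anywhere else?** Covariates in each planned model:
- Stratified log-rank and Cox for first refill (SAP 4.4.1.1): treatment, with the BCVA and prior-injection strata.
- MMRM for BCVA (4.4.2.1): treatment, visit, their interaction, standard baseline BCVA, stratification factors.
- Trimmed-mean ANCOVA and LOCF ANCOVA (4.4.2.1): treatment, standard baseline BCVA, stratification factors.

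Low-luminance BCVA is in none of them. No correlation, regression or subgroup by low-luminance BCVA is defined.

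**2. Could the planned table still show prediction?** Take one arm of 60 patients with assumed values. Let L be standardised low-luminance BCVA at baseline and e a standardised residual uncorrelated with L. Set BCVA change = 3 + 10 × (r × L + √(1 − r²) × e), and keep each patient's change in low-luminance BCVA fixed.

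| r between baseline low-luminance BCVA and BCVA change | Low-luminance change: mean / SD / median | BCVA change: mean / SD |
|---|---|---|
| 0 | 3.0 / 10.0 / 3.77 | 3.0 / 10.0 |
| 0.3 | 3.0 / 10.0 / 3.77 | 3.0 / 10.0 |
| 0.6 | 3.0 / 10.0 / 3.77 | 3.0 / 10.0 |

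The low-luminance summary is the same whether prediction is absent or strong.

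**3. What could an added analysis detect?** Inputs: 180 Implant and 40 ITV patients, and 125 first-refill events (SAP 2.3). For 80% power at two-sided 5%, z = 1.96 + 0.8416 = 2.8016.

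- *Implant v ITV interaction.* The detectable difference in slope is 2.8016 × √(1/180 + 1/40) = 2.8016 × 0.1748 = 0.49 residual SD per SD of the predictor. If the SAP's SD of 10 letters is taken as the residual SD, that is about 4.9 letters per SD. If the 8% dropout assumed for the clogging analysis (Protocol Appendix 21, section 7.4) applied here, it would be 0.49/√0.92 = 0.51.
- *Prognostic main effects, every patient evaluable.* The detectable correlation with later BCVA change is tanh(2.8016/√217) = 0.19 for 220 patients. The detectable HR for first refill per SD is exp(2.8016/√125) = 1.28. Neither allows for overlap with standard baseline BCVA, censoring after rescue or explant, or the excluded site.

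On a common scale, a correlation of 0.188 is 0.188/√(1 − 0.188²) = 0.191 residual SD per SD. The interaction therefore has to be about 0.49/0.191 = 2.6 times as large to be detected.

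**The case against.** The strongest reply is that this is the lowest tier of a study described as exploratory, and that the SAP does what the protocol's outcome measure asks. Much of that stands. Four stronger readings are tempting, and the documents do not support them:

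- *That the protocol promised a formal test.* It says only that utility will be explored, and SAP 4.4 rules out tests beyond the primary endpoint. Estimates with intervals are enough.
- *That the SAP departed from the protocol.* The mismatch begins inside the protocol, between its objective and its own outcome measure. The SAP carries it forward.
- *That the low-luminance data serve no purpose.* Change in low-luminance BCVA is a listed outcome and will be reported, with more than the mean. Only the predictor use is unserved.
- *That the study could answer the benefit question well.* The 0.19 and 1.28 figures describe who does well, not who gains more from the Implant than from injections. The refill model has no ITV comparator at all.

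It can also be said that the biomarker and genetic association objectives have no analysis in this SAP either, and that an association could be run later from the same data. Both are true and keep the point minor. But the SAP does provide for comparable links elsewhere: plots relating refills to BCVA and CFT (4.4.1.1), and the effect of anti-drug antibodies on efficacy and safety (4.6). Low-luminance BCVA has no such line.

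**Conclusion.** The point holds as a mismatch between an objective and its analysis. Followed exactly, the plan yields nothing on low-luminance BCVA as a predictor. This rests on reading the objective as needing a patient-level link to a later benefit, and on no such link appearing in either document. It is a minor point: dose comparison, primary endpoint, sample size and safety are untouched.

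The recoverable information is limited. For benefit relative to monthly injections, only a slope difference of about 0.49 residual SD per SD of the predictor would be detected with 80% power, assuming equal SDs in the two groups and full data. Results should be read as estimates.

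**What to change.** In SAP 4.4.2.1, keep the descriptive table and add a labelled exploratory analysis, reported as estimates with 95% CIs and without tests:

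- **BCVA.** Add low-luminance BCVA at randomization, and its interaction with treatment (pooled Implant v ITV), to the Month 9/10 MMRM. Cross the added terms with visit so that they can be read at the Month 9/10 contrast. The model already adjusts for standard baseline BCVA and the stratification factors.
- **First refill.** In the Implant arms, add low-luminance BCVA at randomization to the stratified Cox model, adjusting for continuous standard baseline BCVA. Describe the result as prognostic for refill durability only.

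Name these two outcomes as the benefit measures for the objective, and state in advance that the interaction will be imprecise. The low-luminance deficit (standard minus low-luminance BCVA) is an optional alternative parameterisation. The documents do not define it. If the 0.19 or 1.28 figure is quoted, label it a prognostic main effect that assumes all patients are evaluable.

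If the sponsor does not want this analysis, reword the objective to describe change in low-luminance BCVA by arm.

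The first option costs two exploratory models on data already collected. The second costs one sentence. Neither needs a new visit or assessment.

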## **Study Design**

### **Description of Study**

Study GX28228 is a Phase II, multicenter, dose-ranging, randomized, active treatment (monthly ITV injection)-controlled study to evaluate the efficacy, safety, and pharmacokinetics of ranibizumab delivered through the Implant using three ranibizumab formulation arms (10 mg/mL, 40 mg/mL, and 100 mg/mL) compared with the control arm (0.5-mg monthly ITV injections of 10-mg/mL formulation) in patients with subfoveal neovascular age-related macular degeneration (nAMD). The study will also evaluate the safety of the RPDS combination product. The study will include pre-screening, screening, and randomization visits followed by a treatment period. Treatment and safety assessment schedules are set.

### **Number of Patients**

Approximately 220 patients at up to 60 sites in the United States will be randomized in a 3:3:3:2 ratio to four treatment arms (60 per each of three Implant treatment arms and 40 to the ITV injection arm) within an approximate 24-month period of time.

### **Target Population**

Patients with subfoveal neovascularization secondary to age-related macular degeneration (AMD) diagnosed within 9 months and treated with ITV anti-VEGF agents will be enrolled in the study.

### **Inclusion Criteria**

Patients must meet the following criteria for study entry:

#### **General Inclusion Criteria**

- Age  $\geq 50$  years
- Willingness and ability to provide signed informed consent and Health Insurance Portability and Accountability Act (HIPAA) authorization
- Willingness and ability to undertake all scheduled visits and assessments
- For sexually active women of childbearing potential, agreement to the use of an appropriate form of contraception (or abstinence) for the duration of the study. A woman is considered not to be of childbearing potential if she is postmenopausal or has undergone hysterectomy and/or bilateral oophorectomy.

For women who are not postmenopausal ( $\geq 12$  months of non-therapy-induced amenorrhea) or surgically sterile (absence of ovaries and/or uterus): agreement to remain abstinent or use single or combined contraceptive methods that result in a failure rate of  $< 1\%$  per year during the treatment period and for at least 30 days after the last dose of study treatment

Abstinence is only acceptable if it is in line with the preferred and usual lifestyle of the patient. Periodic abstinence (e.g., calendar, ovulation, symptothermal, or postovulation methods) and withdrawal are not acceptable methods of contraception.

- Sexually active men are recommended to use a barrier contraceptive method (condom), even if they have been surgically sterilized, for the duration of the treatment period and for at least 30 days after the last dose of study treatment.

#### **Ocular Inclusion Criteria (Study Eye)**

- Newly diagnosed with nAMD within 9 months prior to screening visit
- Patient must have received at least 2 prior anti-VEGF injections (including ranibizumab, bevacizumab, or aflibercept). However, the most recent anti-VEGF injection must have been ranibizumab and must have occurred at least 7 days prior to the screening visit.
- Demonstrated response to prior ITV anti-VEGF treatment, as evidenced by the following:

Decrease in CFT of  $> 50 \mu\text{m}$  since commencing ITV anti-VEGF treatment

**OR**

Stable or improved BCVA since commencing ITV anti-VEGF treatment

- BCVA using ETDRS charts of 20/20-20/200 Snellen equivalent

